3.4.4 Treatment of Relatlimab or Nivolumab-Related Infusion Reactions

Since relatlimab and nivolumab contain only human immunoglobulin protein sequences, they are unlikely to be immunogenic and induce infusion or hypersensitivity reactions. However, if such a reaction were to occur, it might manifest with fever, chills, rigors, headache, rash, pruritus, arthralgias, hypotension, hypertension, bronchospasm, or other allergic-like reactions. All Grade 3 or 4 infusion reactions should be reported within 24 hours to the BMS Medical Monitor and reported as an SAE if it meets the criteria. Infusion reactions should be graded according to NCI CTCAE version 4.0 guidelines. If a subject has an infusion reaction with nivolumab, the relatlimab infusion can be given (without prophylactic medications) if the infusion reaction resolves within 3 hours. For scheduling purposes after a nivolumab infusion reaction, the relatlimab infusion may be given the next day. Prophylactic pre-infusion medications should be given prior to all subsequent nivolumab infusions.

Treatment recommendations are provided below and may be modified based on local treatment standards and guidelines, as appropriate:

For Grade 1 symptoms (Mild reaction; infusion interruption not indicated; intervention not indicated):

- Remain at bedside and monitor subject until recovery from symptoms. The following prophylactic premedications are recommended for future infusions: diphenhydramine 50 mg (or equivalent) and/or acetaminophen/paracetamol 325 to 1000 mg at least 30 minutes before additional study drug administrations.

For Grade 2 symptoms (Moderate reaction requires therapy or infusion interruption but responds promptly to symptomatic treatment [eg, antihistamines, non-steroidal anti-inflammatory drugs, narcotics, corticosteroids, bronchodilators, IV fluids]; prophylactic medications indicated for ≤ 24 hours).

- Stop the infusion, begin an IV infusion of normal saline, and treat the subject with diphenhydramine 50 mg IV (or equivalent) and/or acetaminophen/paracetamol 325 to 1000 mg; remain at bedside and monitor subject until resolution of symptoms. Corticosteroid and/or bronchodilator therapy may also be administered as appropriate. If the infusion is interrupted, then restart the infusion at 50% of the original infusion rate when symptoms resolve; if no further complications ensue after 30 minutes, the rate may be increased to 100% of the original infusion rate. Monitor subject closely. If symptoms recur, then no further study drug will be administered at that visit.

For future infusions, the following prophylactic premedications are recommended:

- Diphenhydramine 50 mg (or equivalent) and/or acetaminophen/paracetamol 325 to 1000 mg should be administered at least 30 minutes before study drug infusions. If necessary, corticosteroids (up to 25 mg of hydrocortisone or equivalent) may be used.

For Grade 3 or 4 symptoms (Severe reaction, Grade 3: prolonged [ie, not rapidly responsive to symptomatic medication and/or brief interruption of infusion]; recurrence of symptoms following initial improvement; hospitalization indicated for other clinical sequelae [eg, renal impairment, pulmonary infiltrates]. Life-threatening, Grade 4: pressor or ventilatory support indicated).

- Immediately discontinue infusion of study drug. Begin an IV infusion of normal saline and treat the subject as follows: Recommend bronchodilators, epinephrine 0.2 to 1 mg of a 1:1000 solution for subcutaneous (SC) administration or 0.1 to 0.25 mg of a 1:10,000 solution injected slowly for IV administration, and/or diphenhydramine 50 mg IV with methylprednisolone 100 mg IV (or equivalent), as needed. Subject should be monitored until the Investigator is comfortable that the symptoms will not recur. Treatment with study drug will be permanently discontinued. Investigators should follow their institutional guidelines for the treatment of anaphylaxis. Remain at bedside and monitor subject until recovery of the symptoms.

In case of late-occurring hypersensitivity symptoms (eg, appearance of a localized or generalized pruritus within 1 week after treatment), symptomatic treatment may be given (eg, oral antihistamine or corticosteroids).

Please refer to [Appendix 4](#) for a complete list of the Nivolumab Management Algorithms.

3.5 Discontinuation of Subjects from Treatment

Subjects **MUST** discontinue investigational product (and non-investigational product at the discretion of the investigator) for any of the following reasons:

- Subject's request to stop study treatment.
- Any clinical AE, laboratory abnormality or intercurrent illness which, in the opinion of the Investigator, indicates that continued participation in the study is not in the best interest of the subject.
- Pregnancy.
- Termination of the study by BMS.
- Loss of ability to freely provide consent through imprisonment or involuntarily incarceration for treatment of either a psychiatric or physical (eg, infectious disease) illness. (Note: Under specific circumstances, and only in countries where local regulations permit, a participant who has been imprisoned may be permitted to continue as a participant. Strict conditions apply and BMS approval is required).
- Inability to comply with protocol requirements.
- Progressive disease (PD; see also [Section 4.3.4](#) for details regarding continuing treatment beyond initial assessment of PD).
- Clinical deterioration as assessed by the investigator.
- Protocol-defined reasons for discontinuation ([Section 4.3.5](#)).

All subjects who discontinue investigational product should comply with protocol-specified follow-up procedures as outlined in [Section 5](#). The only exception to this requirement is when a subject withdraws consent for all study procedures including post-treatment study follow-up or loses the ability to consent freely (ie, is imprisoned or involuntarily incarcerated for the treatment of either a psychiatric or physical illness).

If study treatment is discontinued prior to the subject's completion of the study, the reason for the discontinuation must be documented in the subject's medical records and entered on the appropriate CRF page.

3.6 Post Treatment Study Follow-Up

In this study, overall survival is an exploratory endpoint of the study. Post-treatment study follow-up is of critical importance and is essential to preserving subject safety and the integrity of the study. Subjects who discontinue study treatment must continue to be followed for collection of outcome and/or survival follow-up data as required and in line with Section 5 until death or the conclusion of the study. The only exception to this requirement is when a subject withdraws consent for all study procedures including post-treatment study follow-up or loses the ability to consent freely (ie, is imprisoned or involuntarily incarcerated for the treatment of either a psychiatric or physical illness).

3.6.1 Withdrawal of Consent

Subjects who request to discontinue study treatment will remain in the study and must continue to be followed for protocol specified follow-up procedures. The only exception to this is when a subject specifically withdraws consent for any further contact with him/her or persons previously authorized by subject to provide this information. Subjects should notify the investigator of the decision to withdraw consent from future follow-up **in writing**, whenever possible. The withdrawal of consent should be explained in detail in the medical records by the investigator, as to whether the withdrawal is from further treatment with study drug only or also from study procedures and/or post treatment study follow-up, and entered on the appropriate CRF page. In the event that vital status (whether the subject is alive or dead) is being measured, publicly available information should be used to determine vital status only as appropriately directed in accordance with local law.

3.6.2 Lost to Follow-Up

All reasonable efforts must be made to locate subjects to determine and report their ongoing status. This includes follow-up with persons authorized by the subject as noted above. Lost to follow-up is defined by the inability to reach the subject after a minimum of three documented phone calls, faxes, or emails as well as lack of response by subject to one registered mail letter. All attempts should be documented in the subject's medical records. If it is determined that the subject has died, the site will use permissible local methods to obtain the date and cause of death.

If investigator's use of third-party representative to assist in the follow-up portion of the study has been included in the subject's informed consent, then the investigator may use a Sponsor-retained third-party representative to assist site staff with obtaining subject's contact information or other

public vital status data necessary to complete the follow-up portion of the study. The site staff and representative will consult publicly available sources, such as public health registries and databases, in order to obtain updated contact information. If after all attempts, the subject remains lost to follow-up, then the last known alive date as determined by the investigator should be reported and documented in the subject's medical records.

4 TREATMENTS

All protocol-specified investigational and non-investigational products are considered study drug.

4.1 Study Treatments

Product description and storage information is described in [Table 4.1-1](#). Preparation and administration instructions will be provided separately via site training materials.

For study drugs not provided by BMS and obtained commercially by the site, storage should be in accordance with the package insert, summary of product characteristics (SmPC), or similar documentation.

Table 4.1-1: Product Description and Dosage Form

Product Description and Dosage Form	Potency	Primary Packaging (Volume)/ Label Type	Secondary Packaging (Qty) /Label Type	Appearance	Storage Conditions (per label)
BMS-986016-01 ^a Relatlimab Injection, ■ mg/vial or ■ mg/vial (■ mg/mL)	■ mg/mL	■ mL or ■ mL vial/open label	■ vials/carton/open label	A clear to slightly opalescent, colorless to pale yellow liquid. May contain particles	Store refrigerated, 2-8 °C (36-46 °F) Protect from light Protect from freezing
BMS-936558-01 ^b Nivolumab Injection, ■ mg/vial (■ mg/mL)	■ mg/mL	■ mL vial/open label	■ or ■ vials/carton/open label	Clear to opalescent, colorless to pale yellow liquid. May contain particles	Store refrigerated, 2-8 °C (36-46 °F) Protect from light Protect from freezing

^a Relatlimab; designated as BMS-986016 in the protocol

^b Nivolumab; designated as BMS-936558 in the protocol

4.1.1 Investigational Product

An investigational product, also known as investigational medicinal product in some regions, is defined a pharmaceutical form of an active substance or placebo being tested or used as a reference in a clinical study, including products already with a marketing authorization but used or assembled (formulated or packaged) differently than the authorized form, or used for an unauthorized indication, or when used to gain further information about the authorized form.

The investigational product should be stored in a secure area according to local regulations. It is the responsibility of the investigator to ensure that investigational product is only dispensed to study subjects. The investigational product must be dispensed only from official study sites by authorized personnel according to local regulations.

In this protocol, investigational products are: relatlimab (BMS-986016) and nivolumab (BMS-936558).

4.1.2 Non-investigational Product

Other medications used as support or escape medication for preventative, diagnostic, or therapeutic reasons, as components of the standard of care for a given diagnosis, may be considered as non-investigational products.

In this study, non-investigational product(s) are not applicable.

4.1.3 Handling and Dispensing

The product storage manager should ensure that the study drug is stored in accordance with the environmental conditions (temperature, light, and humidity) as determined by BMS. If concerns regarding the quality or appearance of the study drug arise, the study drug should not be dispensed and contact BMS immediately.

Investigational product documentation must be maintained that includes all processes required to ensure drug is accurately administered. This includes documentation of drug storage, administration and, as applicable, storage temperatures, reconstitution, and use of required processes (eg, required diluents, administration sets).

For treatment visits in Parts C, and D, where both relatlimab and nivolumab are administered, nivolumab will be administered first followed by relatlimab within 30 minutes after completion of the nivolumab infusion. Nivolumab infusion will be administered over 30 minutes. Further details regarding preparation and administration will be provided separately in site/pharmacy training materials.

For non-investigational product, if marketed product is utilized, it should be stored in accordance with the package insert, SmPC, or similar.

4.3 Selection and Timing of Dose for Each Subject

4.3.1 Guidelines for Dose Modification

4.3.1.1 Intrasubject Dose Escalation

Intrasubject dose escalation of relatlimab or nivolumab is not permitted in this study.

4.3.1.2 Dose Reductions

With the possible exception of subjects being treated at a dose level that is subsequently deemed to exceed the MTD, intrasubject dose reduction of relatlimab or nivolumab is not permitted.

4.3.2 Dose Delay Criteria

In some cases, the natural history of select AEs associated with immunotherapy can differ from and be more severe than AEs caused by other therapeutic classes. Early recognition and management may mitigate severe toxicity.

Guidance for Investigators is provided in the current relatlimab and nivolumab Investigator's Brochures.^{58.14} Additionally, management algorithms have been developed to assist Investigators with select toxicities and can be found in [Appendix 4](#).

Toxicities for which management algorithms have been developed include:

- Pulmonary.
- Gastrointestinal.
- Hepatic.
- Endocrine.
- Renal.
- Dermatologic.
- Neurologic.
- Myocarditis.

Subjects who experience the following must have all study drugs(s) delayed:

- Potential DLTs (per definition, are related to study drug) until DLT relatedness is defined.
- Select drug-related AEs and drug-related laboratory abnormalities:
 - \geq Grade 1 pneumonitis.
 - \geq Grade 1 myocarditis.
 - All troponin elevations require a dose delay to allow for prompt cardiac evaluation.
 - \geq Single grade increase shift from baseline (at least to Grade 2) of AST, ALT, and total bilirubin.
 - \geq Grade 2 creatinine.
 - \geq Grade 2 diarrhea or colitis.
 - \geq Grade 2 neurological AE.
 - Grade 4 amylase and/or lipase abnormalities regardless of symptoms or clinical manifestations.
- Any AE, laboratory abnormality, or intercurrent illness, which in the judgment of the Investigator, warrants delaying the dose of study medication.

Subjects may be dosed no less than █ days from the previous dose and no more than █ days from scheduled dose. If an infusion cannot be administered at a scheduled visit, it should be administered as soon as possible. Subsequent dosing visits will follow every █ weeks after the delayed dose. A dose given more than █ days after the intended dose date will be considered a delay. A maximum delay of █ weeks between doses is allowed. Longer delays may be allowed following discussion with the Medical Monitor. Subjects who meet criteria listed in [Section 4.3.5](#) are required to permanently discontinue study drug. All other subjects will be permitted to resume therapy with study drug at the same dose level(s) following resolution of the AE as described in Section 4.3.3.

4.3.3 Criteria to Resume Treatment after Dose Delay

Subjects will be permitted to resume therapy at the same dose level(s) following resolution of the AE to \leq Grade 1 or to baseline within 6 weeks after last dose, with the exception of subjects who meet criteria for permanent discontinuation as specified in Section 4.3.5. Subjects who meet criteria for permanent discontinuation should receive no further study therapy. The following exceptions apply:

- If the toxicity resolves to \leq Grade 1 or baseline $>$ 6 weeks after last dose, but the subject does not otherwise meet the criteria for permanent discontinuation (see Section 4.3.5), and the Investigator believes that the subject is deriving clinical benefit, then the subject may be eligible to resume the study drug(s) following the approval of the BMS Medical Monitor.
- Subjects with a Grade 4 drug-related amylase and/or lipase increase that is not associated with symptoms or clinical manifestations of pancreatitis can be restarted on therapy once the levels have recovered to grade 3 or less, and after consultation with the BMS Medical Monitor.

- Subjects with baseline Grade 1 AST, ALT, or total bilirubin who require dose delays for reasons other than a drug-related hepatic event may resume treatment in the presence of Grade 2 AST, ALT, or total bilirubin.
- Subjects who require dose delays for drug-related elevations in AST, ALT, or total bilirubin may resume treatment when these values have returned to their baseline CTCAE Grade or normal and management with corticosteroids, if needed, is complete, provided the criteria for permanent discontinuation are not met.
- Subjects may resume treatment in the presence of Grade 2 fatigue.
- Subjects with drug-related endocrinopathies adequately controlled with only physiologic hormone replacement may resume treatment.
- Troponin elevations will require the participants to undergo a cardiac evaluation. Following this evaluation, determination of further treatment will be based on the discussion with the BMS Medical Monitor or designee.

4.3.4 Treatment Beyond Disease Progression

Accumulating evidence indicates that a subset of subjects treated with immunotherapy may derive clinical benefit despite initial evidence of PD. Participants treated with relatlimab + nivolumab or with relatlimab alone, will be permitted to continue their study treatment beyond initial investigator assessment of progression, provided the following criteria are met:

- Subject is deriving clinical benefit as assessed by the Investigator.
- Disease progression is not rapid as assessed by the Investigator.
- Subject continues to meet relevant eligibility criteria as determined by the BMS Medical Monitor in discussion with the Investigator.
- Subject tolerates study drug.
- Subject has stable performance status.
- Treatment beyond progression will not delay an imminent intervention to prevent serious complications of disease progression (eg, CNS metastases).
- Subjects have provided written informed consent prior to receiving additional study drug.

The assessment of clinical benefit should be balanced by clinical judgment as to whether the subject is clinically deteriorating and unlikely to receive any benefit from continued treatment. If the Investigator feels that the subject continues to achieve clinical benefit by continuing treatment, the subject should remain on the study and continue to receive monitoring according to the Time and Events Schedule (Table 5.1-2). The decision to continue treatment should be discussed with the BMS Medical Monitor and documented in the study records.

Subjects that meet the above criteria and continue on study therapy beyond initial PD, must discontinue relatlimab (and nivolumab, if part of the combination cohorts) upon the next documented event of PD. A follow-up efficacy assessment should be performed at the next

scheduled evaluation 8 weeks later (but no sooner than 4 weeks later) to determine whether there is continued PD.

4.3.5 Guidelines for Permanent Discontinuation

Subjects meeting any of the following criteria will be required to permanently discontinue all study drug(s) (relatlimab in Part A and B; relatlimab and nivolumab in Parts C and D):

- Any Grade 3 non-skin, drug-related adverse event lasting > 7 days or recurs, with the following exceptions for laboratory abnormalities, drug-related uveitis, pneumonitis, bronchospasm, hypersensitivity reactions, infusion reactions, and endocrinopathies.
- Grade 3 drug-related myocarditis, uveitis, pneumonitis, bronchospasm, or hypersensitivity reaction of any duration.
- Grade 3 infusion reaction that does not return to Grade 1 in 6 hours or less.
- Any Grade 2 drug-related uveitis, eye pain or blurred vision that does not respond to topical therapy and does not improve to Grade 1 severity within the re-treatment period OR requires systemic treatment.
- Any Grade 4 drug-related AE or laboratory abnormality (including but not limited to creatinine, AST, ALT, or Total Bilirubin), except for the following events which do not require discontinuation:
 - Isolated Grade 4 electrolyte imbalances/abnormalities that are not associated with clinical sequelae and are corrected with supplementation/appropriate management within 72 hours of their onset.
 - Grade 4 neutropenia ≤ 7 days in duration.
 - Grade 4 lymphopenia or leukopenia.
 - Isolated Grade 4 lipase and/or amylase abnormalities that are not associated with symptoms or clinical manifestations of pancreatitis.
 - Isolated Grade 4 electrolyte imbalances/abnormalities that are not associated with clinical sequelae and are corrected with supplementation/appropriate management within 72 hours of their onset.
 - Grade 4 drug-related endocrinopathy adverse events, such as adrenal insufficiency, ACTH deficiency, hyper- or hypothyroidism, or glucose intolerance, which resolve or are adequately controlled with physiologic hormone replacement (corticosteroids, thyroid hormones) or glucose-controlling agents, respectively, may not require discontinuation after discussion with and approval from the BMS Medical Monitor.
- Grade 3 drug-related laboratory abnormalities do **not** require treatment discontinuation except:
 - Grade 3 drug-related thrombocytopenia > 7 days or associated with bleeding requires discontinuation.
 - AST, ALT, or bilirubin abnormalities that meet DLT criteria ([Section 3.1.6](#)) (In most cases of AST or ALT elevation meeting DLT criteria study drugs will be permanently discontinued. If the investigator determines a possible favorable benefit/risk ratio that warrants continuation of study drugs, a discussion between the investigator and the BMS Medical Monitor/designee must occur).
 - Elevated troponin that meets DLT criteria ([Section 3.1.6](#)).

- Grade 3 drug-related endocrinopathies adequately controlled with only physiologic hormone replacement do not require discontinuation.
- Any event that leads to dosing delays lasting > 6 weeks from the previous dose **requires discontinuation** with the following **exceptions**:
 - Dosing delays to allow for prolonged steroid tapers to manage drug-related AEs are allowed. Prior to re-initiating treatment in a subject with a dosing interruption lasting > 6 weeks after the previous dose the BMS Medical Monitor must be consulted. Tumor assessments should continue as per protocol even if dosing is delayed. Periodic study visits to assess safety and laboratory studies should also continue every 6 weeks or more frequently if clinically indicated during such dosing delays.
 - Dosing delays lasting > 6 weeks from the previous dose that occur for non-drug-related reasons may be allowed if approved by the BMS Medical Monitor. Prior to re-initiating treatment in a subject with a dosing delay lasting > 6 weeks from the previous dose, the BMS Medical Monitor must be consulted. Tumor assessments should continue as per protocol even if dosing is delayed and subjects must otherwise meet the criteria for continued treatment at the time re-initiation of study therapy is considered. Periodic study visits to assess safety and laboratory studies should also continue every 6 weeks or more frequently if clinically indicated during such dosing delays.
- Any adverse event, laboratory abnormality, or intercurrent illness which, in the judgment of the Investigator, presents a substantial clinical risk to the subject with continued relatlimab or nivolumab dosing.
- PD (see also [Section 4.3.4](#) for details regarding continuing treatment beyond initial assessment of PD).
- Clinical deterioration as assessed by the Investigator.
- Completion of the maximum number of twelve 8-week cycles.

The consideration to re-initiate study therapy in selected cases at any time point after discontinuation could be made on a case-by-case basis after considering the overall benefit/risk profile and in consultation between the Investigator and the study Sponsor. The selected subjects will need to meet eligibility criteria. The original dose and schedule and protocol rules would apply accordingly.

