3.1.5 Re-challenge in Dose Escalation (Part C) and Cohort Expansion (Part D)

If subjects progress during the clinical follow-up period or the survival follow-up period, they could further receive therapy with relatlimab alone or in combination therapy (Re-challenge) as long as the risk:benefit ratio is considered favorable by the Investigator and the Medical Monitor and the following eligibility criteria are met: 1) Subject has confirmed disease progression; 2) Subject has not experienced relatlimab related adverse events leading to permanent discontinuation. The original dose and schedule of therapy and protocol rules will apply. Thus subjects could receive therapy for up to [REDACTED] additional eight-week cycles. Subjects who are re-challenged and who subsequently have an objective response will not be included in the primary analysis of efficacy. Responses to re-challenge will be evaluated in a separate analysis. Subjects will not be re-challenged a second time.

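### Drug-related SJS or TEN below Grade 4 is not a required permanent stop in Section 4.3.5, so Sections 4.3.2 and 4.3.3 permit resumption, whereas the Appendix 4 skin footnote says to stop for good

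*Combined protocol and SAP*

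**What the plan says.** Section 4.3.5 is the mandatory list: meeting any one criterion obliges the site to stop all study drug permanently. Its broad Grade 3 criterion covers "Any Grade 3 non-skin, drug-related adverse event lasting > 7 days or recurs". A second Grade 3 criterion, with no duration condition, names myocarditis, uveitis, pneumonitis, bronchospasm and hypersensitivity reaction. Any Grade 4 drug-related event is a stop, apart from listed exceptions, none of which concerns skin. Neither SJS nor TEN is named.

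Resumption is tied to that list. Section 4.3.2 states: "All other subjects will be permitted to resume therapy with study drug at the same dose level(s) following resolution of the AE". Section 4.3.3 allows resumption at the same dose once the event has returned to Grade 1 or less, or to baseline, within 6 weeks of the last dose, "with the exception of subjects who meet criteria for permanent discontinuation as specified in Section 4.3.5".

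Section 4.3.2 also says that "management algorithms have been developed to assist Investigators with select toxicities", points to Appendix 4 and includes dermatologic toxicity among the topics. Appendix 4 introduces itself as guidance. A footnote to its skin algorithm tells the investigator to withhold therapy and refer the patient if SJS/TEN is suspected, and to discontinue permanently if either is diagnosed. The footnote sentence states no grade.

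**The concern.** The sections that decide who may be re-dosed refer to 4.3.5, and 4.3.5 is silent on SJS/TEN below Grade 4. A site that resumes after recovery can cite 4.3.2 and 4.3.3. A site that stops can cite the Appendix 4 footnote. The mandatory list does not settle the matter, although the sponsor's own algorithm does.

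What is at stake is subject safety and consistent handling across sites. Any effect on the count of adverse events leading to discontinuation would be negligible, and no efficacy analysis is affected.

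**Working it through.** No arithmetic applies. The check takes a drug-related SJS or TEN event below Grade 4 through each rule that could stop it.

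1. **General Grade 3 rule (4.3.5).** Not met, because it is restricted to non-skin events.
2. **Grade 3 events of any duration (4.3.5).** Not met by name. Hypersensitivity reaction is listed, but the protocol does not say that SJS/TEN counts as one, so the outcome would depend on how the site classes the event.
3. **Grade 4 rule (4.3.5).** Not met below Grade 4. At Grade 4 it applies, so there is no gap there.
4. **Grade 2 eye rule and laboratory rules (4.3.5).** Not applicable to the skin diagnosis.
5. **Delay beyond 6 weeks (4.3.5).** Applies only if recovery takes that long. Prolonged steroid tapers for drug-related events are an express exception, and 4.3.3 allows later resumption with Medical Monitor approval.
6. **Investigator judgement.** Section 4.3.5 requires a stop if the investigator judges that an event "presents a substantial clinical risk to the subject with continued relatlimab or nivolumab dosing". Section 3.5 requires one if, in the investigator's opinion, "continued participation in the study is not in the best interest of the subject". Both can reach the case, but they depend on an opinion and not on the diagnosis.
7. **Potential dose-limiting toxicity.** Under the non-hematologic definition in Section 3.1.6.1, a Grade 3 event outside the rash exemption is a dose-limiting toxicity. Section 4.3.2 then requires a hold. Section 3.1.6 sends the subject on to the re-treatment criteria in 4.3.3, so this is a hold and not a permanent stop.

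By grade:

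| Grade | Named hold | Named permanent stop |
|---|---|---|
| 4 | Not needed | Yes, 4.3.5 |
| 3 | Yes, as a potential dose-limiting toxicity, unless rash-exempt | None |
| Below 3, if such grading is possible | None (investigator discretion only) | None |

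With no criterion in 4.3.5 met by the diagnosis itself, 4.3.2 and 4.3.3 permit resumption at the same dose after recovery, unless a judgement or delay criterion is invoked. The Appendix 4 footnote points the other way.

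**The case against.** The strongest reply is that there is no contradiction. Section 4.3.5 is a minimum set of stops, 4.3.2 and 4.3.3 permit resumption without directing it, and Appendix 4 supplies the diagnosis-specific instruction to which 4.3.2 sends the investigator. A site that stops satisfies every text. If Section 9.1.1, which requires the study to be run as the protocol describes, makes Appendix 4 binding, the stop already exists. If Appendix 4 is only guidance, it does not conflict with the mandatory list.

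Much of this stands. The protocol does not instruct anyone to re-treat, and an investigator who reads the footnote will stop. It does not remove the point: the resumption rule makes an exception for 4.3.5 and not for Appendix 4, so the stated rule permits what the algorithm rules out.

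It is also fair that the skin algorithm figure is not shown in the available text, so where the footnote marker attaches cannot be checked, and that the documents do not say how SJS or TEN is graded.

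Two stronger readings are tempting and are not supported.

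- **That skin toxicity as a class was overlooked.** A reader may notice that dermatologic toxicity has an algorithm but no named hold, resume or stop rule in 4.3.2, 4.3.3 or 4.3.5. The Appendix 8 change history for Revised Protocol 07 records that Grade 3 skin was taken out of the delay criteria, so leaving out ordinary skin events looks deliberate. It is not evidence of an error on SJS/TEN.
- **That the gap opens re-challenge.** The adverse-event criterion in 3.1.5 is "Subject has not experienced relatlimab related adverse events leading to permanent discontinuation", which a subject who was allowed to resume could satisfy. Section 3.1 also requires Section 3.3 eligibility and a favorable benefit/risk judgement. Section 3.3.2 excludes conditions that could make study drug hazardous (2f) and, with an exception, a history of life-threatening toxicity from prior immune therapy (2o). The case-by-case re-initiation paragraph that closes 4.3.5 likewise requires eligibility, a benefit/risk review and sponsor consultation. Both routes are secondary.

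**Conclusion.** The point holds as an inconsistency between a mandatory list and the protocol's own guidance. It is confined to drug-related SJS or TEN below Grade 4. Existing safeguards reduce the practical risk without making the diagnosis a required stop.

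Its size cannot be expressed as a rate, because the documents give neither the incidence of SJS/TEN nor the share of cases below Grade 4. The conclusion assumes that some cases can be graded below Grade 4 and that the footnote applies as its sentence reads, without a grade condition. I would class it as a cheap improvement in subject-safety consistency with low practical impact.

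**What to change.** At the next amendment:

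- Add drug-related SJS or TEN, any grade, to the permanent-discontinuation list in 4.3.5. Section 4.3.3 then follows by cross-reference, as does the re-challenge criterion in 3.1.5 where the event is relatlimab-related.
- Add suspected drug-related SJS or TEN to the must-delay list in 4.3.2, matching the footnote's instruction to withhold on suspicion.
- Optionally, state that the re-initiation paragraph at the end of 4.3.5 does not apply after SJS or TEN.
- Leave the handling of other skin events unchanged.

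The sponsor's medical team should confirm the wording. The cost is two list entries and, if wanted, one clause, with no extra subjects or procedures. The downside is that a rare subject loses the option to resume, which the Appendix 4 footnote already advises against.
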